2.2 Secondary

SO 1: To compare the proportion of participants with asthma exacerbations during the 14 days after receipt of LAIV4 or IIV4.

SO 2: To compare the proportion of participants with asthma symptoms and unscheduled albuterol use during the 14 days after receipt of LAIV4 or IIV4.

SO 3: To compare the proportion of participants that experience a clinically significant decrease in Peak Expiratory Flow Rate (PEFR) from baseline during the 14 days after receipt of LAIV4 or IIV4.

2.3 Exploratory

EO 1: To compare the proportions of participants with asthma exacerbations during the 14 and 42 days after receipt of LAIV4 or IIV4, by asthma severity group (Appendix 1).

EO 2: To compare the proportion of participants with asthma symptoms and unscheduled albuterol use during the 14 days after receipt of LAIV4 or IIV4, by asthma severity group.

EO 3: To compare the proportion of participants who experience a clinically significant decrease in PEFR from baseline during the 14 days after receipt of LAIV4 or IIV4, by asthma severity group.

EO 4: To describe and compare changes in Peak Expiratory Flow Rate (PEFR) from baseline (pre-vaccination) PEFR after vaccination over time during the 14 days after receipt of LAIV4 or IIV4, by asthma severity group.

EO 5: To compare change in Childhood Asthma Control Test (c-ACT) score (participants aged 5-11 years) or Asthma Control Test (ACT) score (participants aged 12-17 years) from baseline through 42 days after LAIV4 or IIV4, by asthma severity group

EO 6: To compare asthma symptom days using Preventative Omalizumab or Step-up Therapy for Severe Fall Exacerbations (PROSE) from baseline during the 14 days after vaccination by asthma severity group.

EO 7: To compare rates of medical utilization for asthma-related symptoms during the 14 and 42 days after LAIV4 or IIV4, by asthma severity group.

EO 8: To describe and compare systemic reactogenicity events during the 14 days after receipt of LAIV4 or IIV4, by asthma severity group.

EO 9: To describe and compare serious adverse events after LAIV4 vs. IIV4 during the 42 days after vaccination and assess relatedness to vaccine.

EO 10: To describe and compare asthma symptoms and control among participants with and without a history of allergic rhinitis or hay fever, used as a proxy for allergic versus non-allergic asthma.

3 STUDY OUTCOME MEASURES

3.1 Primary

POM 1.1: Proportion of participants with asthma exacerbations after LAIV4 vs. IIV4 during the 42 days after LAIV4 vs. IIV4 (Day 1 through Day 43)

Note: Asthma exacerbation is defined as: any acute episode of progressively worsening shortness of breath (dyspnea), cough, wheezing, chest tightness, and/or respiratory distress during the 42 days after influenza vaccination for which the patient seeks unscheduled medical attention (e.g., healthcare provider office or Emergency Department visit or hospitalization) or receives a new prescription for systemic corticosteroids.

3.2 Secondary

SOM 1.1: Proportion of participants with asthma exacerbations during the 14 days after LAIV4 vs. IIV4

Note: For the purposes of this outcome measure, the above definition of asthma exacerbation (section 3.1) is modified to include the time period of 14 days after receipt of influenza vaccine (LAIV4 or IIV4)

SOM 2.1: Proportion of participants with asthma symptoms of cough during the 14 days after LAIV4 vs. IIV4

SOM 2.2: Proportion of participants with asthma symptoms of wheezing during the 14 days after LAIV4 vs. IIV4

SOM 2.3: Proportion of participants with asthma symptoms of tightness in chest during the 14 days after LAIV4 vs. IIV4

SOM 2.4: Proportion of participants with asthma symptoms of nighttime awakening during the 14 days after LAIV4 vs. IIV4

SOM 2.5: Proportion of participants with unscheduled albuterol use to treat asthma symptoms during the 14 days after LAIV4 vs. IIV4

SOM 3.1: Proportion of participants who experience a clinically significant decrease in peak flow measurement from baseline during the 14 days after LAIV4 vs. IIV4

Note: A clinically significant decrease in peak flow is defined as: a decrease of $\geq 20\%$ in PEFr from baseline PEFr.

3.3 Exploratory

EOM 1.1: Proportion of participants with asthma exacerbations by asthma severity group (Mild vs. Moderate-Severe) during the 14 days after receipt of LAIV4 or IIV4

EOM 1.2: Proportion of participants with asthma exacerbations by asthma severity group (Mild vs. Moderate-Severe) during the 42 days after receipt of LAIV4 or IIV4

EOM 2.1: Proportion of participants with asthma symptoms of cough by asthma severity group (Mild vs. Moderate-Severe) during the 14 days after receipt of LAIV4 or IIV4

EOM 2.2: Proportion of participants with asthma symptoms of wheezing by asthma severity group (Mild vs. Moderate-Severe) during the 14 days after receipt of LAIV4 or IIV4

EOM 2.3: Proportion of participants with asthma symptoms of tightness in chest by asthma severity group (Mild vs. Moderate-Severe) during the 14 days after receipt of LAIV4 or IIV4

EOM 2.4: Proportion of participants with asthma symptoms of nighttime awakening by asthma severity group (Mild vs. Moderate-Severe) during the 14 days after receipt of LAIV4 or IIV4

EOM 2.5: Proportion of participants with unscheduled albuterol use to treat asthma symptoms by asthma severity group (Mild vs. Moderate-Severe) during the 14 days after receipt of LAIV4 or IIV4

EOM 3.1: Proportion of participants that experience a clinically significant decrease in Peak Flow measurement during the 14 days after vaccination with LAIV4 or IIV4, by asthma severity group (Mild vs. Moderate-Severe)

Note: A clinically significant decrease in peak flow is defined as a decrease of $\geq 20\%$ in PEFr from baseline PEFr.

EOM 4.1: Numerical changes in Peak Flow when compared to baseline during the 14 days after LAIV4 vs IIV4, by asthma severity group (Mild vs. Moderate-Severe)

EOM 4.2: Description of changes in Peak Flow when compared to baseline during the 14 days after LAIV4 vs IIV4, by asthma severity group (Mild vs. Moderate-Severe)

EOM 5.1 Changes in Childhood Asthma Control Test (cACT) scores (participants aged 5-11 years) or Asthma Control Test (ACT) scores (participants aged 12-17 years) from baseline during the 42 days after LAIV4 or IIV4, by asthma severity group (Mild vs. Moderate-Severe)

EOM 6.1: Maximum number of asthma symptom days using Preventative Omalizumab or Step-up Therapy for Severe Fall Exacerbations (PROSE) from baseline during the 14 days after vaccination with LAIV4 or IIV4, by asthma severity group (Mild vs. Moderate-Severe)

EOM 7.1: Rates of medical utilization for asthma-related symptoms during the 14 days after LAIV or IIV4 by asthma severity group (Mild vs. Moderate-Severe)

EOM 7.2: Rates of medical utilization for asthma-related symptoms during the 42 days after LAIV or IIV4 by asthma severity group (Mild vs. Moderate-Severe)

EOM 8.1: Description and comparison of systemic reactogenicity events during the 14 days after LAIV or IIV4 by asthma severity group (Mild vs. Moderate-Severe)

a. Proportions of systemic reactogenicity events during the 14 days after LAIV or IIV4 by asthma severity group

EOM 9.1: Description and comparison of serious adverse events during the 42 days after IIV4 or LAIV4 and performance of a relatedness assessment

a. Proportions of serious adverse events during the 42 days after IIV4 or LAIV4 and performance of a relatedness assessment

EOM 10.1: Description and comparison of asthma symptoms and asthma control (PROSE, and c-ACT/ACT scores) among participants with and without a history of allergic rhinitis or hay fever, as a proxy for allergic versus non-allergic asthma during the 42 days after IIV4 or LAIV4

- a. *Proportions of asthma symptoms and asthma control (PROSE, and c-ACT/ACT scores) among participants with and without a history of allergic rhinitis or hay fever, as a proxy for allergic versus non-allergic asthma during the 42 days after IIV4 or LAIV4*

4 STUDY DESIGN

4.1 Study Description

This study is a prospective, randomized open-label clinical trial that will be conducted during the 2018-2019 and 2019-2020 influenza seasons. During the 2018-2020 seasons, approximately 300 children aged 5-17 years with a physician diagnosis of persistent asthma will be enrolled at Vanderbilt University Medical Center (Lead site), Cincinnati Children’s Hospital Medical Center (contributing site), and Duke University Medical Center (contributing site). In the first season (2018-2019), only children aged 5-11 were eligible; in the second season (2019-2020), the age group was expanded to include children aged 5-17 years. Vanderbilt will enroll about 100 participants, Cincinnati will enroll about 110 participants, and Duke will enroll about 90 participants during these two seasons. In 2018-2019 season, there were 53 children aged 5-11 years enrolled, therefore in 2019-2020 season, we strive to enroll 94, 65, and 88 children at Vanderbilt University Medical Center, Cincinnati Children’s Hospital Medical Center, and Duke University Medical Center, respectively. Children will be followed for up to 42 days following vaccination. Eligible children will be randomized 1:1 to receive either a single intranasal dose of licensed quadrivalent LAIV (LAIV4) or an intramuscular injection of quadrivalent IIV4 (IIV4), stratifying by asthma severity (mild vs. moderate/severe) and age group (5-11, 12-17 years old) at Visit 1. Day 1 is the day of vaccination.

Parents will record the occurrence of fever, solicited adverse events, medical care utilization, and daily symptom assessment on the memory aid along with peak flow measurements. In addition, parents will be contacted through phone call(s), email(s), and/or text messages(s) at visits 2-6 (See Protocol “Figure 1. Participant Flow Chart” and “Table 1: Schedule of Events”).

4.2 Sample Size and Power

This study aims to enroll approximately 300 participants (approximately 100 from Vanderbilt, approximately 110 from Cincinnati, and approximately 90 from Duke). We assume that the proportion of participants with asthma exacerbation(s) in 42 days after vaccination is 12% after LAIV4 and IIV4 [1]. We also assume that ~10% of the children may drop out, yielding a total sample of at least 270 (135 LAIV4 and 135 IIV4).

Our research hypothesis is that the proportion of participants with asthma exacerbation(s) in the LAIV4 (experimental group) will not be higher than in the IIV4 group (control group). The power estimate is shown below, given delta of 10% and one-sided alpha is set at 5% level.

Proportion of participants with asthma exacerbation(s) in control IIV4 group (pc)	Proportion of participants asthma exacerbation(s) in LAIV4 experimental group (pe)	Estimated power to reject H0: pe – pc >= 10%
---	--	---

12%	12%	81.1%
-----	-----	-------

The null hypothesis is that the proportion of participants with asthma exacerbation(s) in the LAIV4 group will be inferior (higher) than the proportion in the IIV4 group. The null hypothesis will be rejected (and delta margin noninferiority claimed) when the upper bound of the 95% one-sided confidence interval for the pe minus pc is less than 10%. IBM SPSS SamplePower software version 3.0.1 was used for the power calculation which was not adjusted for stratifying by site.

4.3 Randomization

Participants will be randomized (1:1) to receive either a single intranasal dose of licensed quadrivalent LAIV4 or an intramuscular injection of quadrivalent inactivated influenza vaccine (IIV4), stratifying by asthma severity (mild vs. moderate/severe) in both influenza seasons and age group (5-11 and 12-17 years old) in the second influenza season (2019-20). The permuted block randomizations will be done separately for each site (i.e., Vanderbilt University Medical Center, Duke University Medical Center and Cincinnati Children's Hospital Medical Center), with varying block size of either 4 or 6. Each site may have more than one clinic to recruit participants, and proportions of participants with mild or moderate/severe asthma can vary by clinics. Randomization will be accomplished using the REDCap System, hosted at Vanderbilt. Since this is a web-based system, it is easily accessible to the other collaborating sites as well. This study will be open label and study staff and subjects will not be blinded to treatment arm assignments.

5 PARAMETERS OF ANALYSIS

5.1 Data Collection and Storage

Data will be handled according to the study manual of procedures (MOP) and entered by study personnel onto REDCap database.

5.2 Analytic Issues

There are three sites participating in the study (Vanderbilt, Cincinnati, Duke) and analysis of the primary objective of the non-inferiority hypothesis will be tested and stratified by site to account for site variation. The first secondary objective will be stratified by site as well, though the rest of the secondary and exploratory objectives will not be stratified by site. There will be one primary objective and first secondary objective evaluated on a one-sided alpha at 0.05 level and assessed based on overlapping two-sided 90% binomial confidence upper boundaries. All other analyses are two-sided and alpha at 0.05 level. There will be no adjustments to the alpha level for all secondary and exploratory analyses except the first secondary objective.

6 ANALYSIS POPULATIONS

6.1 Intent-to-Treat (ITT) Population:

The ITT Population includes any participant that was enrolled, randomized into the study, and received a study vaccine at Visit 1.

6.2 Per Protocol Population for 43 Days:

The Per Protocol Population for 43 days (PP43) is a subset of the ITT Population. This is defined as all participants who were randomized, vaccinated, completed study procedures

through day 43, had no protocol deviations that are likely to affect the objectives, and did not receive a second dose of influenza vaccine before day 43.

6.3 Per Protocol Population for 15 Days:

The Per Protocol Population for 15 days (PP15) is a subset of the ITT Population. This is defined as all participants who were randomized, vaccinated, completed study procedures through day 15, had no protocol deviations that are likely to affect the objectives, and did not receive a second dose of influenza vaccine before day 15.

The Per Protocol Population for 43 days is the primary analysis population for the Primary Objective. Statistical analyses for the Primary Objective will be performed for the ITT population and the Per Protocol for 43 days, or the ITT Population only if no participants are excluded from the Per Protocol Population. The Per Protocol population for 15 days is the primary analysis population for the Secondary Objectives. Statistical analyses for the Secondary Objectives will be performed for the ITT population and Per Protocol population for 15 days, or the ITT Population only if no participants are excluded from the Per Protocol Population. The list of protocol deviations that meet criteria for exclusion from analysis is provided in Appendix 2.

In the ITT population, participants will be analyzed according to randomization assignment, rather than treatment group. If applicable, sensitivity analyses on primary and secondary objectives will be done on datasets defined by treatment group. For example, if a participant was assigned to LAIV4 and inadvertently received IIV4 that participant would be reassigned to the IIV4 treatment group in the sensitivity analyses.

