8.1 Primary Objective

The primary objective (PO 1) of the study is to compare proportions of participants with asthma exacerbation(s) during the 42 days after LAIV4 versus IIV4 in children with asthma aged 5-17 years.

The hypothesis for this primary objective is that the proportion of participants with asthma exacerbation(s) after LAIV4 is non-inferior to the proportion of participants with asthma exacerbation(s) after IIV4 (the proportion of participants with asthma exacerbation(s) after vaccination is not higher in the LAIV4 group vs. the IIV4 group). Asthma exacerbations will be assessed from day 1 through day 43. This information is captured on the memory aid forms and recorded in the REDCap database. *Any unscheduled medical attention (e.g., healthcare provider office, emergency department visit, hospitalization) due to any acute episode of progressively worsening shortness of breath/ dyspnea, cough, wheezing, chest tightness, and/or respiratory distress OR received a new prescription for systemic corticosteroids after LAIV4 vs. IIV4 during the 42 days post-vaccination will be counted as asthma exacerbations yes (1) and asthma exacerbations no (0) otherwise, for this analysis.*

This objective will be assessed using a one-sided non-inferiority test with the alpha level set at 0.05 and non-inferiority margin of 10%. The null hypothesis is LAIV4 is inferior to IIV4 in regard to the proportion of subjects having asthma exacerbations during the 42 days post-vaccination (i.e., LAIV4 will have a higher proportion of asthma exacerbations compared to IIV4).

$$H_0: \text{LAIV4} - \text{IIV4} \geq 0.1 \text{ (10\%)}$$

The alternative hypothesis is LAIV4 is non-inferior to IIV4 in regard to the proportion of subjects having asthma exacerbations during the 42 days post-vaccination.

$$H_a: \text{LAIV4} - \text{IIV4} < 0.1 \text{ (10\%)}$$

The proportions will be compared between LAIV4 versus IIV4 using a Cochran-Mantel-Haenszel method in a stratified analysis by site to control for three sites at the one-sided alpha 0.05 level. The upper bound of 95% one-sided confidence interval for the proportion difference between two vaccine groups will be used to make this assessment and we will reject H_0 if it's less than 10%.

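### The non-inferiority claim rests on PP43 as primary population, and the plan does not say what is concluded if ITT disagrees

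*SAP*

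**What the plan says.** SAP section 6 and protocol 8.2 both name PP43 as the primary population for the primary objective. On ITT, the SAP says that "Statistical analyses for the Primary Objective will be performed for the ITT population and the Per Protocol for 43 days", and that ITT is used by itself only when PP43 excludes nobody. The decision is a "one-sided non-inferiority test with the alpha level set at 0.05 and non-inferiority margin of 10" percent (SAP 8.1). SAP 4.2 and 8.1 and protocol 8.1 and 8.2.2 all compare one upper bound with that margin. None of them names the population, asks for agreement, or deals with disagreement.

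ITT is everyone randomised and vaccinated. To stay in PP43 a child must also complete procedures through Day 43, have no deviation likely to affect the objectives, and be one who "did not receive a second dose of influenza vaccine before day 43". SAP Appendix 2 adds receipt of an investigational product or a non-study vaccine as grounds for exclusion. SAP 4.3 says that "study staff and subjects will not be blinded to treatment arm assignments".

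Protocol 7.1 says that data gathered before a withdrawal remain in use for analysis. SAP 8.1 codes the outcome as 1 for a recorded exacerbation and 0 for everything else. The only sensitivity analysis (SAP 10) regroups children by vaccine received.

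**The concern.** Completion, an early second dose and receipt of another product are all settled after randomisation, by families and staff who know the vaccine given. Protocol 7 also lets the investigator withdraw a child because of a new clinical finding, for non-compliance or for other reasons. An exacerbation could plausibly lead to any of these.

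The clearest case is a child with an exacerbation on Day 10 who is lost on Day 25. The endpoint has occurred and is known. Protocol 7.1 says such data will be used, yet the completion rule removes the child from PP43. The event survives only in ITT, which has no stated part in the claim. In a safety trial, losing events from the LAIV4 arm favours the conclusion that the sponsor hopes to reach.

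**Working it through.** **Inputs.** Margin 10 points and one-sided alpha 0.05 (SAP 8.1). The assumed proportion "in 42 days after vaccination is 12% after LAIV4 and IIV4" (SAP 4.2). About 300 enrolled 1:1, so 150 per arm, and 135 per arm after 10% dropout (SAP 4.2, 4.3). The rule is the Wald bound of protocol 8.2.2:

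U = (pe − pc) + 1.645 × √[pe(1 − pe)/ne + pc(1 − pc)/nc]; pass if U < 10 points.

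**1. The plan's own power.** SE = √(2 × 0.12 × 0.88/135) = 0.03955. Then 0.10/0.03955 − 1.645 = 0.883, and Φ(0.883) = 81.1%. The stated figure reproduces, and 135/0.9 = 150, so the sample size is not in question.

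**2. Can the two populations disagree?** Suppose 15 children per arm are excluded from PP43.

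| Population | LAIV4 v IIV4 | Difference | SE | U (points) | Result |
|---|---|---|---|---|---|
| PP43 | 20/135 v 16/135 | 2.96 | 4.13 | 9.76 | pass |
| ITT, excluded had 3 v 1 events | 23/150 v 17/150 | 4.00 | 3.92 | 10.45 | fail |
| ITT, excluded had 2 v 1 | 22/150 v 17/150 | 3.33 | 3.88 | 9.71 | pass |
| ITT, excluded had 3 v 2 | 23/150 v 18/150 | 3.33 | 3.96 | 9.85 | pass |

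Near the margin one child can be enough. ITT at 24/150 v 18/150 gives 10.58 and fails; excluding one LAIV4 child with an exacerbation gives 23/149 v 18/150, which is 9.97 and passes.

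**3. How often would it matter?** Simulation: 200,000 trials per setting, 150 per arm, 10% of each arm excluded, all outcomes known in ITT. The exclusion ratios (children with an exacerbation relative to those without) are assumptions. The table gives the false-claim rate at the margin, 22% v 12%.

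| Ratio in LAIV4, IIV4 | PP43 decides | Both must pass |
|---|---|---|
| 1, 1 | 5.2% | 3.8% |
| 2, 2 | 6.7% | 4.0% |
| 3, 3 | 7.5% | 4.0% |
| 2, 1 | 10.3% | 4.9% |
| 3, 1 | 15.5% | 5.2% |

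With true rates of 12% v 12% and exclusion unrelated to outcome, power is 81.2% on PP43, 84.5% on ITT and 79.3% when both must pass.

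**4. What if lost children are coded 0?** Take the same 20 and 16 events and count all 15 excluded per arm as event-free. ITT is then 20/150 v 16/150: difference 2.67, SE 3.75, U = 8.83. That is easier to pass than PP43 (9.76), because the counts stay the same while both denominators grow. A both-must-pass rule then adds almost nothing, and the false-claim rates return to about 10% and 15%.

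These figures use the unstratified bound. SAP 8.1 stratifies by site, and the documents give no site-level rates.

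**The case against.** A per-protocol primary set is an ordinary choice for non-inferiority, and the ITT result will be produced, so a disagreement would be visible. A reader might infer that the plan decides on PP43 alone. The documents do not say so: the decision rules name no population. What can be shown is the absence of a rule for disagreement.

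A reader might also infer that the PP43 exclusions in general are open to influence by arm. Several are not. Eligibility and severity assessment (Appendix 2, items 1 and 2) belong to Visit 1 before randomisation, and a wrong product (item 5) is fixed at vaccination. The second-dose route concerns only children aged 5–8 who need two doses and receive dose 1 in the study. Protocol 4.7.3 makes them eligible after four weeks and in general asks them to wait until after Day 43, so the window is roughly Days 29–42. That leaves non-completion as the main route, with early second doses and other products as minor ones.

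The illustration is also an edge case. PP43 starts 0.24 points below the margin, one more LAIV4 event fails it (21/135 gives 10.58), and reversal needs 3 v 1 events among the excluded. Disagreement can run the other way: at 12% v 12% with unrelated exclusion, ITT alone passes in 5.2% of trials and PP43 alone in 1.9%.

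All of this narrows the point, but it leaves the gap open. Visibility does not prevent a claim, and nothing in the plan says that a failed ITT analysis would.

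**Conclusion.** The point stands as a missing rule: as written, non-inferiority may be claimed on PP43 while ITT fails. The documents do not support saying that PP43 is biased, or in which direction. With exclusion unrelated to outcome, PP43 keeps a size of about 5%. With children who exacerbate excluded two or three times as often in both arms, size is 6.7% or 7.5%. It reaches about 10% or 15% only if that excess is confined to LAIV4, and the documents give no figure for any of these ratios. The protection from requiring both populations depends on how lost children are handled in ITT. Under the present coding of everything unrecorded as 0, the requirement would do almost nothing. The change is worth making because both analyses are already planned and the loss of power is about two points.

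**What to change.** 1. In SAP 6 and 8.1, state: *Non-inferiority will be claimed only if the one-sided 95% upper bound is below 10% in both PP43 and ITT.*
2. In ITT, count every exacerbation recorded before withdrawal, in line with protocol 7.1. Do not code children lost before Day 43 without a recorded event as 0. Handle them by a stated missing-outcome method such as multiple imputation, with a tipping-point check.
3. Tabulate PP43 exclusions by arm, reason and exacerbation status at exclusion. SAP 7.2 already plans a flow chart by vaccine group and a CONSORT diagram, but not this breakdown.
4. Restate power: about 79% at 12% v 12% if exclusion is unrelated to outcome, in place of 81.1%.

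The cost is about two points of power, a short SAP text including the imputation model, and one table. No new data are needed.
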